5.2. Exclusion Criteria

Subjects are excluded from the study if any of the following criteria applies at either screening or, if applicable, at randomization (Visit 3):

1. Current diagnosis of any severe complication of celiac disease, such as RCD-I or RCD-II, enteropathy-associated T-cell lymphoma (EATL), ulcerative jejunitis, or GI perforation.
2. Diagnosis of any chronic, active GI disease other than celiac disease, such as active, untreated peptic ulcer, eosinophilic esophagitis, erosive esophagitis, ulcerative colitis or Crohn's disease, microscopic colitis, irritable bowel syndrome, small intestinal bacterial overgrowth, tropical sprue, or other GI and non-GI disorder or prior GI surgery that may, in the Investigator's opinion, interfere with the assessment of symptoms of abdominal pain, diarrhea, or other components of celiac disease.
3. Any known, symptomatic food allergy that, in the opinion of the Investigator, may interfere with the conduct or interpretation of the study.
4. Presence of any of the following related to infection:
 - a. Active acute infection with flu-like symptoms such as fever, cough, or shortness of breath; or active infections requiring systemic (intravenous or intramuscular) treatment (antibiotics, antifungal, or antiviral).
 - b. Active GI infection, including *H. pylori*.
 - c. History of tuberculosis (TB) except for successful chemoprophylaxis for positive TB tests.
 - d. Positive Interferon Gamma Release Assay (IGRA) test at screening. Subjects with potential false-positive tests may have the test repeated. If chest X-ray is also clear, they may be enrolled.

- e. History of an opportunistic infection typical of those seen in immunocompromised patients (e.g., herpes zoster, systemic candida infection, or systemic fungal infection) within 3 years prior to screening.
5. Any of the following laboratory test abnormalities at screening or Visit 1 (Day -28):
 - a. Alanine aminotransferase (ALT) and aspartate aminotransferase (AST) >3 times the upper limit of normal (ULN).
 - b. Hemoglobin <9 g/dL (<90 g/L in SI units).
 - c. Platelet count <100,000 mm³ (<100/L).
 - d. White blood cell count <3,000 cells/mm³ (<3.0 ×10⁹/L).
 - e. Creatinine >1.5 mg/dL.
 - f. Hemoglobin A1c (HbA1c) >9% (>90 mmol/mol) in subjects with a concurrent diagnosis of Type 1 or Type 2 diabetes.
6. Use of systemic immune suppressants (including systemic or GI topical steroids) during the screening or single-blind placebo run-in period.
7. Required use of a prohibited medication (see Section 6.5.1) during the screening or single-blind placebo run-in period.
8. Current diagnosis or recent history of cancer within the past 5 years, except successfully treated basal cell or squamous cell carcinoma, cervical carcinoma-in-situ, or early-stage prostate cancer.
9. Known or suspected exposure to COVID-19 infection in the 4 weeks before screening.
10. Administration of a live vaccine within 14 days prior to randomization and the first administration of study drug at Visit 3.
11. History or presence of any clinically significant disease that, in the opinion of the Investigator, may confound the subject's participation and follow-up in the clinical trial or put the subject at unnecessary risk, including but not limited to: uncontrolled hypertension (BP ≥180/110 mm/Hg), unstable angina, Class II congestive heart failure or major fluid overload, coronary angioplasty or myocardial infarction within the past 6 months, clinically significant arrhythmias or electrocardiogram (ECG) abnormalities, severe chronic pulmonary disease, or any renal, hematologic, GI, immunologic, dermatologic, neurologic, or psychiatric disease.
12. History of significant substance or alcohol abuse during the 12 months prior to screening as obtained by medical record and/or subject report.
13. Hepatitis B virus (HBV), hepatitis C virus (HCV), or human immunodeficiency virus (HIV) positive test results.
14. Females who are pregnant or planning to become pregnant during the study period, or who are currently breastfeeding.
15. Participation in another investigational drug or device study or treatment with an investigational drug within 30 days or 5 half-lives, whichever is longer, prior to screening.
16. Any other reason that, in the opinion of the Investigator, may prevent the subject from safely participating in the study or complying with protocol requirements, including the endoscopies and biopsies.

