8.1. All Laboratory Tests

The maximum amount of blood collected from each subject over the duration of the study is expected not to exceed 400 mL over a period of approximately 9 months. This estimation does not include repeat or unscheduled samples, which may be taken for safety reasons or for technical issues with collected samples.

All laboratory tests to be conducted at in-office visits are listed as follows.

Screening Visit (within 28 days before Visit 1)

- Chemistry: calcium, ALT, AST, albumin, total and direct bilirubin, sodium, potassium, blood urea nitrogen (BUN), creatinine, chloride, CO₂, glucose, total protein, alkaline phosphatase (ALP) (if ALP is >3 x ULN, test 5' nucleotidase or GGT), magnesium, phosphorus
- Complete blood count (CBC): hemoglobin, hematocrit, platelets, white blood cell count (WBC) with differential, red blood cell count (RBC), mean corpuscular volume (MCV), mean corpuscular hemoglobin concentration (MCHC), mean cell hemoglobin (MCH)
- Urinalysis (dipstick and microscopic)
- HbA1C (subjects with diagnosed Type 1 or Type 2 diabetes only)
- HLA DQ2/8 (as needed)
- Testing for HIV, HBV and HCV for exclusion as follows:
 - HIV: positive antibody to p24 antigen (Ab-p24Ag) for human immunodeficiency virus (HIV) 1 or 2 confirmed by positive HIV 1/2 Western blot
 - HBV: HBsAg, anti-HBc total (IgM and IgG) confirmed by positive HBV DNA, anti-HBs
 - HCV: HCV antibody confirmed by positive HCV RNA
- IGRA
- *H. pylori* stool test
- Serum pregnancy test (all WOCBP only)
- FSH/LH for women with suspected menopause (i.e., not surgical menopause)
- Serum IgA
- Anti-tTG IgA and IgG, anti-DGP IgA and IgG

Visit 1 (Single-blind run-in Week -4)

- Chemistry (same tests as screening)
- CBC (same tests as screening)
- HbA1C (subjects with diagnosed Type 1 or Type 2 diabetes only)
- Urinalysis (same tests as screening)
- Stool and urine gluten tests
- Urine pregnancy (WOCBP only)

Visit 2 (Single-blind run-in Week -2)

- Stool and urine gluten tests

- Urine pregnancy (WOCBP only)

Visit 3 (Week 0/Day 1)

- Chemistry (same tests as screening)
- CBC (same tests as screening)
- Urinalysis (same tests as screening)
- Stool and urine gluten tests
- Urine pregnancy test (WOCBP only)
- Anti-tTG IgA, anti-DGP IgA
- Ferritin, iron, TIBC, vitamins D, B12, folate
- Serum biomarkers (e.g., IL-15)
- Trough concentration of PRV-015
- ADA

Visit 4 (Week 2/Day 15)

- Stool and urine gluten tests
- Trough concentration of PRV-015
- ADA

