8.7.3 Clinical Laboratory Tests

8.7.3.1 Serum Chemistry, Hematology, Urinalysis, Pregnancy Tests

Laboratory safety variables include hematology, clinical chemistry and urinalysis panels. The complete list of laboratory tests is included in Table 4 below.

Table 4. Clinical Laboratory Tests

Serum Chemistry (Units)	Hematology (Units)	Urinalysis
ALT (IU/L)	Basophils (109/L)	Appearance
AST (IU/L)	Basophils/Leukocytes (%)	Bilirubin
Albumin (g/L)	Eosinophils (109/L)	Color
Alkaline Phosphatase (IU/L)	Eosinophils/Leukocytes (%)	Glucose
Total Bilirubin (umol/L)	Mean cell hemoglobin (MCH)	Ketones
Direct Bilirubin (umol/L)	Mean Corpuscular HGB Concentration	Leukocyte Esterase
Calcium (mmol/L)	(g/L)	Nitrite
Carbon Dioxide (mmol/L)	Mean Corpuscular Hemoglobin (fmol)	Occult Blood
Chloride (mmol/L)	Mean Corpuscular Volume (fL)	pH
Creatinine (umol/L)	Hematocrit (%)	Protein
Glucose (mmol/L)	Hemoglobin (g/L)	Specific Gravity
Magnesium (mmol/L)	Lymphocytes (109/L)	Urobilinogen
Phosphorus (mmol/L)	Lymphocytes/Leukocytes (%)	
Potassium (mmol/L)	Monocytes (109/L)	Urine Microscopic
Total Protein (g/L)	Monocytes/Leukocytes (%)	
Sodium (mmol/L)	Neutrophils (109/L)	Urine pregnancy
Urea Nitrogen (mmol/L)	Neutrophils/Leukocytes (%)	test
	Platelets (109/L)	
	Red Blood Cell Count (1012/L)	

	White Blood Cell Count (109/L)	
--	--------------------------------	--

Clinical laboratory parameters will be obtained at times indicated in the SoA in Appendix 11.1. Cutoff values considered to be potentially clinically important (PCI) for selected laboratory tests are outlined in Appendix 11.2.

A summary of subjects meeting any of the PCI criteria for post-baseline laboratory measurements will be provided by treatment group. All clinical laboratory test results will be provided in data listings with PCI criteria flagged.

Separate data listings for urine and serum pregnancy tests will be provided in female subjects of childbearing potential.

Potential Hy's law (ALT or AST > 3 x ULN concurrent with total bilirubin > 2 x ULN at the same visit) will be summarized by treatment group and listed. eDish plots will be used to present subjects potentially meeting Hy's law.

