11.2 PCI criteria for Hematology, Serum Chemistry, Urinalysis

		C	conventional Uni	its	SI Units					
Test Name	Sex	Reference Range	Units	PCI Criteria	Reference Range	Units	PCI Criteria			
Hematology			1							
	М	13.5 – 17.5	g/dL	< 8.1 or > 20	135 - 175	g/L	< 81 or > 200			
Hemoglobin	F	12.0 – 15.5	g/dL	< 8.1 or > 20	120 - 155	g/L	< 81 or > 200			
Hemoglobin				2 point decrease from baseline			20 point decrease from baseline			
White Cell Count		4.0 – 11.0	x10E3/uL	< 2.1 or > 35	4.0 - 11.0	x10E9/L	< 2.1 or > 35			
Eosinophils (Abs)		0.0 - 0.6	x10E3/uL	>=3	0.0 - 0.6	x10E9/L	>=3			
Neutrophils (Abs)		1.5 - 7.7	x10E3/uL	<1	1.5 - 7.7	x10E9/L	<1			
Platelets	17	150 - 450	x10E3/uL	< 100 or > 1000	150 - 450	x10E9/L	< 100 or > 1000			
Serum Chemistry										
	М	5.9 - 8.0	g/dL	< 4.0	59 – 80	g/L	< 40			
Protein (Total)	F	6.2 - 7.9	g/dL	< 4.0	62 - 79	g/L	< 40			
	М	4.03 - 5.51	g/dL	< 2.0	40.3 – 55.1	g/L	< 20			
Albumin	F	4.02 - 5.24	g/dL	< 2.0	40.2 - 52.4	g/L	< 20			
	М	6.7 – 33.4	IU/L	>=3X ULN	6.7 – 33.4	IU/L	>=3X ULN			
ALT	F	6.6 - 22.9	IU/L	>=3X ULN	6.6 - 22.9	IU/L	>=3X ULN			
	М	12.4 – 33.0	IU/L	>= 3X ULN	12.4 – 33.0	IU/L	>= 3X ULN			
AST	F	11.8 – 25.7	IU/L	>= 3X ULN	11.8 – 25.7	IU/L	>= 3X ULN			
	М	36.1 – 124.2	ĮU/L	>= 3XULN	36.1 – 124.2	IU/L	>= 3XULN			
AP (AlkPhos)	F	35.6 - 118.3	ĮU/L	>= 3XULN	35.6 - 118.3	IU/L	>= 3XULN			
	М	0.24 - 1.49	mg/dL	>=2X ULN	4.10 - 25.48	umol/L	>=2X ULN			
Bilirubin (Total)	F	0.19 - 1.13	mg/dL	>=2X ULN	3.25 - 19.32	umol/L	>=2X ULN			

			Conventional Ur	nits		SI Units	
Test Name	Sex	Reference Range	Units	PCI Criteria	Reference Range	Units	PCI Criteria
	М	20 - 32	mmol/L	< 18 or > 40	20 - 32	mmol/L	< 18 or > 40
Bicarbonate	F	19 - 29	mmol/L	< 18 or > 40	19 - 29	mmol/L	< 18 or > 40
	М	8.2 - 23.8	mg/dL	> 40	2.93 - 8.50	mmol/L	>14.25
BUN (Urea)	F	5.9 - 21.4	mg/dL	> 40	2.11 - 7.64	mmol/L	>14.25
	М	8.5 - 10.3	mg/dL	< 6 or > 12	2.13 - 2.58	mmol/L	< 1.5 or > 3
Calcium	F	8.5 – 10.2	mg/dL	< 6 or > 12	2.13 – 2.55	mmol/L	< 1.5 or >
	М	98 – 108	mmol/L	< 90 or > 125	90 – 108	mmol/L	< 90 or > 125
Chloride	F	99 - 107	Mmol/L	< 90 or > 125	99 - 107	mmol/L	< 90 or > 125
	М	0.63 - 1.20	mg/dL	>=1.5	55.69 - 106.08	umol/L	>=132
Creatinine	F	0.51 - 0.96	mg/dL	>=1.5	45.08 - 84.86	umol/L	>=132
Glucose		< 140	mg/dL	> 500	< 7.8	mmol/L	> 27.75
	М	1.8 – 2.2	mg/dL	<1.22 or >4.87	0.74-0.90	mmol/L	<0.5 or >2
Magnesium	F	1.7 – 2.2	mg/dL	<1.22 or >4.87	0.70 - 0.90	mmol/L	<0.5 or >2
	М	2.1 - 4.6	mg/dL	< 0.5	0.68 - 1.49	mmol/L	< 0.5

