11.3 PCI criteria for Vital Signs and Weight

Vital signs		
HR	≤50 bpm and decrease from baseline ≥20 bpm	
	≥120 bpm and increase from baseline≥20 bpm	
SBP	≤95 mmHg and decrease from baseline ≥20mmHg	
	≥160 mmHg and increase from baseline ≥20 mmHg	
DBP	≤45 mmHg and decrease from baseline ≥10 mmHg	
	≥110 mmHg and increase from baseline ≥10 mmHg	

Weight	≥5% increase from baseline	FDA Feb 2007	
	≥5% decrease from baseline		

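### Exclusion 5f gives two incompatible HbA1c limits: >9% is about >75 mmol/mol, not the printed >90 mmol/mol

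*Protocol*

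**What the plan says.** Exclusion 5 in Protocol section 5.2 lists laboratory abnormalities at screening or Visit 1, any one of which excludes. Item 5f reads "Hemoglobin A1c (HbA1c) >9% (>90 mmol/mol) in subjects with a concurrent diagnosis of Type 1 or Type 2 diabetes". Item 5b, in the same list, reads "Hemoglobin <9 g/dL (<90 g/L in SI units".

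The test is scheduled where the criterion applies. Protocol section 8.1 lists "HbA1C (subjects with diagnosed Type 1 or Type 2 diabetes only") under both the screening visit and Visit 1.

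Nothing else in the documents fixes the HbA1c limit. SAP section 8.7.3.5 only lists the results, and the PCI table in SAP section 11.2 has no HbA1c row.

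A second item in the list bears on a side point. Item 5a reads "Alanine aminotransferase (ALT) and aspartate aminotransferase (AST) >3 times the upper limit of normal (ULN"). The SAP's safety rules name either enzyme: "Potential Hy's law (ALT or AST > 3 x ULN concurrent with total bilirubin > 2 x ULN at the same visit") in section 8.7.3.1, and separate ALT and AST rows in section 11.2, each at 3 x ULN or above.

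**The concern.** An exclusion threshold has to give one answer for each subject. In 5b and 5d the leading value is the limit and the parenthesis restates it correctly in other units. In 5f the parenthesis is a different and looser limit. A site working from the percentage and a site working from the SI figure would decide differently on the same subject, and the looser figure admits subjects with poorer diabetic control.

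Two later steps need a single limit. SAP section 8.3 lists the eligibility criteria not met, by subject. SAP section 8.1.5 names randomization of an ineligible subject among the deviations that may remove someone from the Per-Protocol set, on which the primary analysis is repeated.

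**Working it through.** **Inputs.** From Protocol 5.2: 9% and 90 mmol/mol (5f); 9 g/dL and 90 g/L (5b). The conversion is assumed: mmol/mol = (HbA1c% − 2.15) × 10.929.

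**Trying to reproduce the printed 90.**
- 9.0%: (9 − 2.15) × 10.929 = 74.9 mmol/mol.
- Allowing for rounding of 9%: 8.95% gives 74.3 and 9.05% gives 75.4.
- Treating 9.49% as if it were 9%: 80.2.
- Slope without the offset: 9 × 10.929 = 98.4.
- Plain multiplication: 9 × 10 = 90.

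Only the last gives 90. Multiplying by ten is right for hemoglobin in 5b (9 g/dL × 10 = 90 g/L) but does not convert HbA1c. That the figure in 5f arose this way is a guess, and the mismatch does not depend on it.

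**Reverse direction.** 90 / 10.929 + 2.15 = 10.4%. As a check on the proposed figure, 75 / 10.929 + 2.15 = 9.01%.

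**Size of the gap.** 90 − 74.9 = 15.1 mmol/mol, or 10.4 − 9.0 = 1.4 percentage points of HbA1c. For example, 9.5% is (9.5 − 2.15) × 10.929 = 80.3 mmol/mol and 10% is 85.8. Both are excluded by the percentage and pass the SI figure.

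**Range over the assumption.** Three straight lines of the form % = slope × mmol/mol + intercept:

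| Line assumed | 9% in mmol/mol | 90 mmol/mol in % |
|---|---|---|
| 0.0915x + 2.15 (standard) | 74.9 | 10.4 |
| 0.0927x + 1.73 | 78.4 | 10.1 |
| 0.0989x + 0.88 | 82.1 | 9.8 |

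Under none of them is 9% equal to 90 mmol/mol. The narrowest band of disagreement is 9.0% to 9.8%.

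**Item 5a.** The readings 'both enzymes raised' and 'each enzyme has this limit' differ only when exactly one enzyme is above 3 x ULN. With the female ranges in SAP 11.2, 3 x ULN is 3 × 22.9 = 68.7 IU/L for ALT and 3 × 25.7 = 77.1 IU/L for AST. A woman with ALT 80 (3.5 x ULN) and AST 60 (2.3 x ULN) is eligible under the first reading and excluded under the second. Whether the SAP settles the reading can be checked by comparing the rest of list 5 with the PCI limits:

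| Test | Exclusion 5 | PCI limit, SAP 11.2 |
|---|---|---|
| Platelets | <100,000/mm³ | <100 x10E3/uL |
| Creatinine | >1.5 mg/dL | ≥1.5 mg/dL |
| Hemoglobin | <9 g/dL | <8.1 g/dL |
| White cells | <3,000/mm³ | <2.1 x10E3/uL |

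Platelets match, creatinine nearly so, and hemoglobin and white cells do not. The PCI table does not mirror the exclusion list, so it cannot show what 5a was meant to say.

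**The case against.** The strongest defence is practical. The percentage comes first and is evidently the intended limit, so most sites would apply it. The documents do not show that any site worked in mmol/mol, and only diabetic subjects are concerned. On the Per-Protocol set, SAP 8.1.5 does not remove an ineligible subject automatically: the deviation must be judged likely to affect interpretation, and that judgement is recorded before unblinding. The SAP also describes conduct in the past tense (sections 8.6.1.5 and 8.9), so a correction may reach few or no subjects. All of this stands, and it limits the size of the point. It does not make the two limits agree, and no other text tells a site or a blinded reviewer which to use.

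A reader might infer more from 5a: that it wrongly requires both enzymes to be raised, contradicts the SAP, and would inflate the PCI counts. The documents do not support that. Under a lead-in that makes any listed abnormality exclusionary, the wording can naturally mean that each enzyme carries the limit. The SAP rules are safety flags, not eligibility rules, and the Hy's law rule also needs raised bilirubin.

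It is true that the transaminase PCI limits carry no change-from-baseline condition, whereas the low heart-rate limit does ("≤50 bpm and decrease from baseline ≥20 bpm"). But a spurious count needs a subject with one raised enzyme who is not stopped by the investigator-judgement exclusions (11 and 16) and whose value stays raised until the first post-baseline chemistry at Week 4, eight weeks after Visit 1. Nothing suggests that such subjects would fall unevenly across randomized arms.

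**Conclusion.** Exclusion 5f is wrong as written. It carries two limits about 15 mmol/mol, or 1.4 percentage points, apart, and subjects with diabetes between about 9.0% and 10.4% are classified differently by each. This rests on the standard HbA1c conversion, which is not in the documents; the conflict remains under the other lines tried, with a band no narrower than 9.0% to 9.8%. Taking >9% as the intended limit is an inference from its leading position and from the pattern in 5b and 5d.

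The correction is minor. The number of subjects affected is unknown and probably small, and it would be wrong to infer that ineligible subjects were in fact enrolled. Power, alpha and the primary mITT analysis are unaffected; the only efficacy link is through the repeat analysis on the Per-Protocol set. Item 5a is an ambiguity of wording, not a demonstrated error.

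**What to change.** - **5f:** keep >9% and replace the parenthesis with >75 mmol/mol. This is a protocol amendment and needs IRB/IEC approval before implementation (Protocol section 10.1.1). Apply it prospectively and tell the sites.
- **If enrolment has closed:** before unblinding, record in the subject classification document that >9% is the governing limit when eligibility deviations are judged for the Per-Protocol set. A value in the disputed band would still have to pass the existing test of likely effect on interpretation before the subject is removed.
- **Optional:** in the same amendment, reword 5a as 'ALT or AST >3 times ULN', if either enzyme is meant to exclude.

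The cost is one amendment with its approvals and a site letter, or a single pre-unblinding note if recruitment is over. No new data are needed. Prospectively, a site that had used the SI figure might see a few more diabetic screen failures, and the 5a wording could add a few for subjects with one raised enzyme.

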5.3. Lifestyle Considerations

Subjects are required to maintain the same diet as they have been adhering to during the entire study.

Subjects are required to refrain from blood donation, illicit drug use (per applicable laws), and alcohol abuse (based on Investigator's judgment) throughout the duration of the study.

5.4. Screen Failures

Screen failures are defined as subjects who consent to participate in the clinical study but do not enter the single-blind placebo run-in phase. Randomization failures are defined as those who enter the single-blind placebo run-in phase but do not meet the inclusion criteria or meet any exclusion criteria at Visit 3 and therefore are not randomized to a treatment group.

A minimal set of screen failure information is required to ensure transparent reporting of screen failure subjects to meet the Consolidated Standards of Reporting Trials (CONSORT) publishing requirements and to respond to queries from regulatory authorities. Minimal information includes demography, screen failure details, eligibility criteria, and any screening SAE.

Individuals who are screen failures may be rescreened once. Rescreened subjects will be assigned the same subject number as for the initial screening. Subjects who are rescreened should be reconsented at the time of the rescreening. Subjects who have entered the run-in period or were randomization failures will not be rescreened.

6. Study Treatment

Study treatment is defined as any investigational product or placebo to be administered to a study subject according to the study protocol.

6.1. Study Drug Administered

At each visit, each subject will receive 4 injections for a total volume of 6 mL. Depending on the assigned treatment group, the amount of active PRV-015 and/or placebo injected will vary as outlined below to administer the desired dose while maintaining the double blind.

Name	PRV-015	Placebo
Type	Biologic	Protein-free solution
Unit Dose Strength(s)	100 mg/mL with 2 mL deliverable volume in a 10 mL vial	N/A 1 ml placebo solution in 5 mL vials
Dosage Levels and Frequency	a. 100 mg q2w b. 300 mg q2w c. 600 mg q2w	Placebo q2w
Volume per Dose	a. 1 mL active × 1 syringe, 1 mL placebo × 1 syringe, 2 mL placebo × 2 syringes b. 1 mL active × 1 syringe, 2 mL active × 1 syringe, 1 mL placebo × 1 syringe, 2 mL placebo × 1 syringe c. 1 mL active × 2 syringes, 2 mL active × 2 syringes	1 mL placebo × 2 syringes 2 mL placebo × 2 syringes
Route of Administration	SC injection	SC injection
Sourcing	Provided centrally by the Sponsor	Provided centrally by the Sponsor

Packaging and Labeling	Provided in glass container and labeled according to local requirement	Provided in glass container and labeled according to local requirement
-------------------------------	--	--

Duration of Study Treatment and Participation

The duration of study participation for each subject is approximately 9 months, including \leq 4 weeks of screening period, 4 weeks of placebo run-in period, 24 weeks of double-blind treatment period, and 4 weeks of final safety follow-up period.

6.2. Preparation/Handling/Storage/Accountability

PRV-015 will be supplied in a glass container and should be stored frozen at a temperature -30°C (± 10 °C). Prolonged exposure to light should be avoided. The placebo solution should be stored refrigerated at 5 ± 3 °C.

An unblinded pharmacist at the site will prepare 4 syringes labeled for each subject. All syringes will be labeled with appropriate measures to maintain the blind.

Further guidance and information for the final disposition of unused study drugs are provided in the Pharmacy Manual.

6.3. Measures to Minimize Bias: Randomization and Blinding

All subjects will be centrally assigned to randomized study drug (placebo or 1 of 3 doses of PRV-015) after the single-blind, placebo run-in period using an Interactive Voice/Web Response System (IVRS/IWRS). Before the study is initiated, the telephone number and call-in directions for the IVRS and/or the log-in information and directions for the IWRS will be provided to each site.

Subjects will be randomly assigned in a 1:1:1:1 ratio, stratified by VH:CD of <2 or ≥ 2 (assessed during the placebo run-in period) and by the CeD PRO Abdominal Symptoms domain score of <3 or ≥ 3 at baseline, using the average of the Abdominal Symptoms domain scores over the last week of the run-in period immediately before randomization. The Investigator, Sponsor, and subjects will remain blinded to each subject's assigned study drug throughout the course of the study. In order to maintain this blind, an otherwise uninvolved pharmacist or equivalent staff member will be responsible for the reconstitution and dispensation of all study drug and will ensure that there are no differences in time taken to dispense following randomization.

In the event of a Quality Assurance audit, the auditor(s) will be allowed access to unblinded study drug records at the site(s) to verify that randomization/dispensing has been done accurately.

Emergency Unblinding

The Investigator may unblind a subject through the IVRS/IWRS at any time for an emergency where the treatment assignment is important for the subject's medical care. However, if at all possible, it is recommended that the Investigator should consult with the Medical Monitor or Sponsor Medical Lead before unblinding. If the Investigator encounters difficulty in unblinding, the local clinical research associate can be reached for assistance.

